**Breach of Confidentiality**

Information will be kept under lock and key with password protection on the computer. Coding will be used with no patient identifiers attached to confidential information. Even with these precautions, breach of confidentiality is a risk.

**Use of Questionnaires:**

Some questions in the questionnaires may make subjects feel uncomfortable. Subjects may choose not to answer any question with which he/she feels uncomfortable.

**Page numbers from a sponsor's protocol/grant may be referenced in 9.9 and 9.10.**

9. **Special Precautions. Describe the planned procedures for protecting against or minimizing potential risks. If appropriate, include the standards for termination of the participation of the individual subject. Discuss plans for ensuring necessary medical or professional intervention in the event of adverse effects to the subjects.**

If side effects or discomforts do occur, [name] and [name] will try to minimize and treat these by irrigating the treated sinus with saline to remove the Arista, Nexfoam, Sinufoam, and Nasopore. Also, removal of excess hemostatic agents during irrigation will lessen the risk of obstruction, embolization and death. The risk of embolization and death are only present if a hemostatic agent is directly injected or placed onto an open vessel. This will not be happening in this study. Hemostatic agents will only be topically applied to sinuses post operatively.

**Use of questionnaires:**

Subjects may choose not to answer any question with which he/she feels uncomfortable

**Protocol Title:** Analysis of hemostatic agents compared to physiologic hemostasis

---

10. Reproductive Risks.

- a. Please list the pregnancy category of any drugs or N/A.

N/A

- b. Please describe any reproductive risk associated with any part of the research study. Include any data from other studies (animal or human).

Some research medications or procedures can cause severe birth defects, mental retardation to an unborn baby, or loss of the unborn baby. If patients take part in a research study that includes a drug or medical procedure, they must be willing to have a pregnancy test done before beginning their participation. Patients must avoid becoming pregnant while they take part in the research study.

11. Data Safety Monitoring

Federal regulations require that when appropriate, the research protocol makes adequate provisions for monitoring the data to ensure the safety of participants. Monitoring should be commensurate with risks and with the size and complexity of the research, and could range from no plan needed to an independent data safety monitoring board. Please refer to SLU Guidelines for Data and Safety Monitoring as you complete the questions below.

- a. Is there a Data Monitoring Committee (DMC) or Board (DSMB)? N/A

If yes, please provide the following information (labeled a-g): a) the composition of the board (degrees/qualifications of members), b) whether the board is independent from the sponsor and research team or not, c) frequency of meetings and issuance of reports to sites, d) assurance that the board is reviewing aggregate safety data and making recommendations regarding study continuance, e) provisions for ad hoc meetings if needed, f) who is reviewing SAEs in real time (MD or DO), and g) stopping/halting rules (if any exist).

A DSM charter can be referenced for all items except for "f) who is reviewing SAEs in real time."

If no, please justify why not.

- b. Is there a Data Safety Monitoring Plan (DSMP)? N

Note, if all relevant plan information is included in DSMB question above, select 'Yes' and state "see above" in the answer box.

**Protocol Title:** Analysis of hemostatic agents compared to physiologic hemostasis

---

If yes, provide details (labeled a-e) including: a) what types of data or events are captured and how are they documented, b) who is monitoring data, their independence/affiliation with the research and their degrees/qualifications, c) frequency of aggregate data review, d) who is reviewing SAEs in real time (MD or DO), and e) stopping/halting rules (if any exist).

If no, please justify why not.

All procedures are standard of care. Risks are minimal.

12. In case of international research (research outside of the U.S. or research on international populations (non-U.S.)), describe qualifications/preparations that enable you to evaluate cultural appropriateness and estimate/minimize risks to subjects. Include whether research is sensitive given cultural norms.

a. State any local laws/regulations governing Human Subjects Research in the country(ies) you will conduct the research and attach any relevant approvals. If none, state N/A.

b. Will there be language barriers and if so, how will they be addressed?

Note: If materials are to be distributed to subjects in their native language, please follow SLU's Guidance For Studies Involving Non-English Speaking Subjects.

**NOTE: Export control laws include the transfer of technical information and data, as well as information and technology to foreign nationals. If this study has international components, contact the SLU Export Control Officer for direction on whether export control policies apply.**

---

**\*\*\* Benefits/Alternatives, Procedures to Maintain Confidentiality and Privacy \*\*\***

**10. Benefits/Alternatives**

a) **Benefits.** Describe the potential benefit(s) to be gained by the subjects and how the results of the study may benefit future subjects and/or society in general. Indicate if there is no direct benefit to the participants.

a.) Subjects will not benefit from the research.

b.) Society may benefit from research findings because they will provide physicians with evidence of the effects and side effects of available hemostatic agents, and help them make well educated decisions about which agents are best in practice.

b) **Alternatives.** Describe any alternative treatments and procedures available to the subjects should they choose not to participate in the study. If no such alternatives exist, please state that the alternative is nonparticipation. For some studies, such as record reviews, a description of alternatives would not be

**Protocol Title:** Analysis of hemostatic agents compared to physiologic hemostasis

---

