**1. Background**

**Protocol Title:** Analysis of hemostatic agents compared to physiologic hemostasis

---

Page numbers from a sponsor's protocol/grant may be referenced in 1a and 1b.

- a) **Provide an introduction and background information. Describe past experimental and/or clinical findings leading to the formulation of the study, if applicable. Investigator Initiated studies must cite references in the response provided or attach a bibliography. *\*?HELP?\****

In this study we wish to determine if the use of hemostatic agents after endoscopic sinus surgery is superior to no agent at all. We will treat patients with one of many different FDA approved hemostatic agents in one of their nostrils and compare it to a side in which no therapy is applied. We will then evaluate qualities of the patient's recovery (synechia formation, granulation, edema, infection, and time spent debriding the sinuses) in response to intervention.

Functional endoscopic sinus surgery (ESS) is a safe, commonly performed procedure primarily in an outpatient setting. One of the most prevalent complications is post-operative epistaxis. To prevent this nasal packing is often employed. Traditionally non-absorbable packing was employed; yet, this has fallen out of favor with most otolaryngologists considering the great discomfort of the packing, especially upon removal (von Schoenberg). In addition to this, with removal of non-absorbable packing interruption of the wound bed is inevitable. This has led to a paradigm shift towards absorbable packing, which are biomaterials that provide substrate to stimulate clotting. Absorbable hemostatic agents tend to spare the mucosa and are less painful upon removal (Maccabee). However, absorbable packing comes with the possible drawback of increased rates of synechia formation secondary to initiation of local inflammation (Valentine). Standard of care is no packing, one of these types of absorbable packing, or removing packing.

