causing rapid hemoconcentration of platelets, serum proteins and fibrinogen, leading to clotting that limits and controls bleeding and edema. It is FDA approved and filed under K120958.

f). Sinufoam, Arista, Nasopore, Nexfoam, Posisep and PosiSep X are all being used for purposes approved following sinus surgery by the FDA.

**Protocol Title:** Analysis of hemostatic agents compared to physiologic hemostasis

---

purposes approved following sinus surgery by the FDA.

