## 2. Purpose of the study

- a) Provide a brief lay summary of the project in <200 words. The lay summary should be readily understandable to the general public.

Our study is a prospective comparison between absorbable hemostatic agents as a group and the body's natural hemostatic ability without aid of therapy in patients undergoing bilateral sinus surgery with or without septoplasty.

Page numbers from a sponsor's protocol/grant may be referenced in 2b and 2c.

- b) List your research objectives (specific aims & hypotheses of the study).

The purpose of this study is to evaluate the efficacy of absorbable hemostatic agents in comparison with physiologic hemostasis after endoscopic sinus surgery. We aim to determine the relative efficacy of hemostatic agents to halt epistaxis and compare this with the degree of epistaxis observed without therapy. Also will evaluate objective healing parameters.

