**Please save frequently**

- c) Describe the study design (e.g., single/double blind, parallel, crossover, control, experimental, observational, etc.). If the study is investigator-initiated, a timeline for individual subject recruitment, follow-up, and analysis for the study is required. Also, indicate if the subjects will be randomized.

Our study is a prospective comparison between absorbable hemostatic agents as a group and the body's natural hemostatic ability without aid of therapy in patients undergoing bilateral sinus surgery with or without septoplasty.

We calculated the sample size and power analysis in the following way:

Given the number of statistical tests, we calculated a Bonferonni correction to set the alpha for the analysis at 0.017 (alpha originally at .05 divided by the number of tests = .05/30 = 0.017). Using G-Power statistical software, power analyses were completed using the Means: Wilcoxon-Mann-Whitney test (two groups). Given alpha at 0.017 and Power at 0.80, we determined that a total of 244 participants (122 in the control group, 122 in the hemostatics group) would be needed to detect a medium effect size (d=0.5). Since one nostril will be used as the control and the therapy applied to the other side, the number of participants needed drops to 122.

Based on previous studies, we conservatively expect a dropout rate of 15%. In order to maintain the same number of participants, we would need to enroll a total of 144 participants

Postoperatively, patients will rate subjective symptoms such as nasal obstruction, bleeding,

**Protocol Title:** Analysis of hemostatic agents compared to physiologic hemostasis

---

pain, and nasal discharge on a scale ranging from 1-10, of which 10 is the most severe. Similarly, the treating physicians on endoscopic examinations will rate objective measures such as mucosal edema, infection, time spent debriding, and synechiae formation. (Please see the attached patient and physician questionnaires) Patient questionnaires will be completed on postoperative days #1, 2, 7, and 14. Surgical healing outcomes will be noted during routine postoperative visits 1 and 2 weeks after surgery. Expected total duration of each subjects' participation is 6 weeks. Total subject accrual should take no longer than one year. Data analysis will take up to three months. Estimated time of completion is 03/2018.

d) **If subjects will be given placebo, please justify placebo use. \*?HELP?\***

N/A

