**If No, explain what SLU will NOT participate in:**

**Please save frequently**

Page numbers from a sponsor's protocol/grant may be referenced in 3b, 3c, and 3d.

- b) **Describe all the procedures, from screening through end-of-study, that the human subject must undergo in the research project, including study visits, drug treatments, randomization and the procedures that are part of standard of care. Specify which procedures are for research and which are standard of care. Please note: The box below is for text only. If you would like to add tables, charts, etc., attach those files in the Attachment section (#16).**

a.) Patients will have (standard of care) Endoscopic Sinus Surgery.  
 b.) Each patient will receive a hemostatic agent in one nostril and nothing in the other nostril.  
 c.) Products will be placed in patients' post-operative sinus cavities at the end of the procedure according to company recommended instructions. Essentially all products placed in the middle meatus are allowed to remain there until absorbed or removed at a post operative visit on weeks 1, 2, and 6. Post-operative irrigations (Standard of Care) will remove much of the material. Any residual material is removed in the office on normal, (Standard of Care) post-operative debridement on weeks 1, 2, and/or 6.  
 d.) Subjects will provide subjective pre- and post-operative data, such as rating their pain, bleeding, obstruction, and discharge on days 0, 1, 2, 7, and 14 (Standard of Care).  
 e.) Patients will be given a questionnaire packet pre-operatively (Research Related). Questionnaires will include post-operative data on days 0, 1, 2, 7, and 14. They are asked to bring completed questionnaires on standard post-operative visits.  
 f.) The physician will record objective and subjective data (synechiae, edema, infection, granulations, and time spent debriding) upon regular reexamination of the sinuses after surgery, at post-operative visits on weeks 1, 3, and 6. All procedures are standard clinical care.  
 g.) Follow up visits will conform to standard clinical care; patients will be seen in the physician's clinic.

**Protocol Title:** Analysis of hemostatic agents compared to physiologic hemostasis

---

clinic.

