- c) If the proposed study is a clinical trial where a drug, vaccine, device or other treatment is compared to a placebo group or comparison treatment group, what are the guidelines or endpoints by which early decisions regarding efficacy or lack of efficacy can be made? For example, it may be reasonable to stop enrollment on a study when efficacy has already been clearly demonstrated, to avoid unnecessary enrollments of additional subjects. Alternatively, it may be reasonable to stop enrollment when it is clear that efficacy will never be demonstrated, given the statistical power of the study as designed. Describe the guidelines that are in place to assist in making these determinations, if relevant to the proposed study.

If side effects or discomforts do occur, [name] and/or [name] will try to minimize and treat these by irrigating the treated sinus with saline to remove the Arista, Nexfoam, Sinufoam, Nasopore, Posiseq, or Posiseq X.

- d) Describe how data analysis will be performed (statistical tests, methods of evaluating data) and indicate the smallest group/unit for which separate reporting will occur. For studies involving a questionnaire, if data and reliability information are available, please describe or provide references. For full board, unfunded studies describe sample size determination and power analysis. If none, please justify.

Means and standard deviations will be obtained for data collected from patients and the physician. These outcomes will be used for comparative evaluation of hemostatic agents (n=144) against no therapy. Statistics will include descriptive statistics and a non-parametric ANOVA comparing the questionnaire patient data and the physician data followed by Post-hoc multiple comparisons.

Please save frequently

- e) State if deception (including incomplete disclosure of study purpose/procedures) will be used. If so, describe the nature of the deception and provide a rationale for its use. Also, describe debriefing procedures or justify a waiver of the requirement to debrief. NOTE: for studies using deception, an alteration of consent must be justified in the Informed Consent section of the protocol (#13) and the debriefing script/statement must be uploaded in the Attachments section (#16). See IRB Deception Guidelines.

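### The aims and benefit statement point to conclusions about individual agents, but the design and sample size support only agents as a group versus no agent

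*Combined protocol and SAP*

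**What the plan says.** Three places point toward conclusions about individual agents.

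- Section 2b (objectives): "We aim to determine the relative efficacy of hemostatic agents to halt epistaxis and compare this with the degree of epistaxis observed without therapy".
- Section 10a (benefits), introduced as something from which society may benefit: the results will "help them make well educated decisions about which agents are best in practice".
- Section 3d (data analysis): a non-parametric ANOVA "followed by Post-hoc multiple comparisons". The contrasts are not named.

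The design is described differently. Section 2a refers to "absorbable hemostatic agents as a group", and section 2c calls the study a "prospective comparison between absorbable hemostatic agents as a group and the body's natural hemostatic ability without aid of therapy". The sample size in 2c is for two groups, treated and control, with d=0.5.

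On allocation, section 1a says "We will treat patients with one of many different FDA approved hemostatic agents in one of their nostrils" and its item f) lists six: "Sinufoam, Arista, Nasopore, Nexfoam, Posisep and PosiSep X are all being used for purposes approved following sinus surgery by the FDA". Section 3b says "Each patient will receive a hemostatic agent in one nostril and nothing in the other nostril". The prompt in 2c asks whether subjects will be randomized, and the answer does not say. No rule for choosing the agent and no number per agent appears anywhere.

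**The concern.** The untreated nostril gives each patient an internal control for agent versus nothing. It does not do so for one agent versus another. Each patient receives a single product, so agents can be compared only across different patients. The requirement in section 8h that disease be similar on both sides protects the side-to-side comparison, not this one. With no stated assignment rule, the choice of agent could follow the treating physician, the calendar period or the severity of disease.

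Two errors are then open. A chance difference among small subgroups could be taken as a product recommendation. A failure to separate the agents could be taken as evidence that they are equivalent. The sample size guards against neither.

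**Working it through.** **Inputs.** d=0.5, power 0.80, the printed alpha of 0.017, the quotient 0.05/30, 122 patients, 15% dropout and 144 enrolled (all section 2c). Six agents (sections 1a and 5). 144 entered as evaluable (section 8b). The equal split over agents is an assumption.

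**Formula.** Noncentral-t power for the Wilcoxon-Mann-Whitney test, with normal-parent efficiency 3/π: effective n* = 3n/π per group, df = 2n* − 2, noncentrality = d√(n*/2).

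**The plan's own figure.** For n=122, n* = 116.5 and the noncentrality is 0.5 × √58.25 = 3.816. At one-sided alpha 0.05/30 = 0.00167 the critical value is 2.966 and power is 0.801; 121 gives 0.797. So 122 reproduces, from the quotient and one-sided. At the printed 0.017 the same method gives 75 per group (one-sided) or 89 (two-sided). That mismatch is a separate matter. Dropout: 122/0.85 = 143.5, rounded up to 144, which agrees.

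**Patients per agent.** 122/6 = 20.3; 144/6 = 24.

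**Power for two agents differing by d=0.5, two-sided.** For n=20, n* = 19.1 and the noncentrality is 0.5 × √9.55 = 1.545. For n=24, n* = 22.9 and it is 1.693. Six agents give 6 × 5/2 = 15 pairs.

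| alpha | n=20 | n=24 |
|---|---|---|
| 0.05, unadjusted | 33% (0.325) | 38% |
| 0.017, as printed | 18% | 23% |
| 0.05/15, all pairs | 7% | 9% |

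An unequal split leaves some agents with fewer patients; at 10 each, power is 18% at 0.05. For 80% power at d=0.5 the same method needs 67, 89 or 122 per agent at the three alphas, which is 402, 534 or 732 patients over six agents.

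**Size of a chance ranking.** The expected range of six independent standard normal values is 2.534. With six identical agents and 20 patients each, the expected gap between the best and worst observed mean is 2.534/√20 = 0.57 SD (2.534/√24 = 0.52 SD with 24). Both exceed the d=0.5 that the trial is built to detect. In simulation with true agent means evenly spaced over 0.5 SD, the truly best agent ranks first in about 48% of trials at n=20 and 50% at n=24.

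**One overall test across agents.** If one agent is better by 0.5 SD and the other five are equal, the F-test noncentrality at n=20 is 20 × 0.25 × 5/6 = 4.17 on 5 and 114 df. Power at 0.05 is 29%.

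**Effect of using within-patient differences.** If the untreated side is the same on average across agents, the standardized effect becomes 0.5/√(2(1−ρ)), where ρ is the correlation between sides. The documents do not give ρ. At n=20 and alpha 0.05:

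- ρ=0: effect 0.354, power 19%
- ρ=0.3: effect 0.423, power 25%
- ρ=0.5: effect 0.500, power 33%, the same as for treated-side scores
- ρ=0.7: effect 0.645, power 49%

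**The case against.** The plan does not say in so many words that it will rank products. The sentence in 10a answers a form question on benefit to society and is conditional; it is neither a hypothesis nor a commitment to report. The design is stated as pooled, and the background section asks whether agents are superior to none. That stands, and it makes this a matter of scope rather than a fault in the main comparison. It does not dispose of section 2b, which is an aim, and whose wording puts the relative efficacy of the agents before the comparison with no therapy.

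A reader might infer from 3d that agent-versus-agent tests are planned. The text does not establish this. The sentence before it describes agents against no therapy, and assessment day is another possible factor. The count of 30 tests can be filled without any agent contrast: 4 symptoms × 5 days (section 3b) plus 5 physician measures (3b) × 2 visits (2c) = 20 + 10 = 30. On the other side, agents against nothing has only two groups and would need no post-hoc step. If agents are not meant, the statements in 2b and 10a have no analysis behind them.

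A reader might also infer that raw scores will be analysed without regard to the untreated side. Section 3d does not say which quantity is analysed. Likewise confounding is possible but not shown, because the documents do not record how agents were chosen.

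Finally, power for two agents can be put as low as 4-6% by using 0.05/30. That is not the alpha the plan prints, and it applies a 30-test correction to a set of 15 pairs. The table above uses the printed alpha and the natural correction for pairs instead.

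**Conclusion.** The point holds in a limited form. The aim in 2b and the benefit statement in 10a suggest agent-level conclusions that neither the design nor the sample size supports. With 20-24 patients per agent, power for the plan's own effect size is at most 38% without any adjustment, 18-23% at the printed alpha, and 7-9% with correction for all pairs, against the 80% used for the pooled contrast. Contrasts between agents are also between patients, with no stated assignment rule, so they are potentially confounded.

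The figures rest on an equal split, a normal parent distribution and two-sided tests; an unequal split makes some pairs worse. Pooling the agents is a fair choice, and the pooled comparison with no therapy is not affected by this point.

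**What to change.** In 2b and 10a, limit the confirmatory conclusion to agents as a group versus no agent, and remove the statement about which agents are best.

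In 3d, name the post-hoc contrasts. State that any agent-level result is exploratory and consists of:

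- each agent's treated-minus-untreated difference with a 95% confidence interval, for outcomes rated separately by side;
- one test of heterogeneity of those differences across the six agents, with a note that a non-significant result does not show equivalence;
- the number of patients per agent and an account of how agents were chosen;
- no ranking of products.

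Section 2c does not say whether patients score each nostril separately, so the plan should list the outcomes to which the side difference applies.

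The cost is wording, one small exploratory table and a more modest claim. Differencing loses some power for comparing agents if the correlation between sides is below 0.5, and gains some above it. Enrolment need not change. The continuing-review category marked in the form is the one for studies with only data analysis remaining, and the changes proposed here are to analysis and reporting.
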